16.6 Appendix 6 Guidance for Ophthalmic Monitoring

Fingolimod has previously been associated with a two-fold increase in the risk of macular edema in renal transplant patients receiving cyclosporine. There have been macular edema cases in the treatment of fingolimod, therefore careful ophthalmic monitoring is being implemented to permit early detection of this event, should it occur.

A complete ophthalmic examination by an ophthalmologist will be conducted in accordance with [Table 8-1](#). Similar assessments must be performed at an unscheduled ophthalmology visit for any participant who presents with new visual symptoms or decrease in visual acuity.

The following assessments will be performed at the ophthalmic examinations:

1. Best corrected visual acuity using a visual acuity chart with equal spacing between letters and between lines
2. Optical Coherence Tomography (OCT) is required for participants at Screening and Month 3 visit. OCT may be required at other visits to evaluate macular thickness under the investigator's discretion.

At baseline, if there is a suspicion of macular edema and increased central foveal thickness by OCT, then a fluorescein angiogram may be performed (at the discretion of the ophthalmologist). Participants with diagnosed macular edema at Screening should be deemed a screening failure and should not be enrolled. Patients with history of uveitis and patients with diabetes mellitus are at an increased risk of macular edema and may require more frequent ophthalmic evaluations, per investigator's discretion.

During the study, participants with a diagnosis of macular edema during the study must interrupt the study drug. These patients must be followed-up 1 month and 3 month after diagnosis of macular edema and more frequently if needed based on the ophthalmologist's judgement. Further ophthalmologic evaluations until such time as resolution is confirmed or no further improvement is expected by the ophthalmologist (based on a follow up period of not less than 3 months). These evaluations will include repeat best corrected visual acuity, fundus examination and OCT. Fluorescein angiography (FA) is performed at the discretion of the ophthalmologist. If the participant does not show definite signs of improvement on examination by specialist testing (e.g. OCT, FA) 6-8 weeks after interruption of study drug, then therapy for macular edema in conjunction with an ophthalmologist experienced in the management of this condition should be initiated.

An interruption or discontinuation of the study drug should be clearly documented and reflected on eCRF. AE/SAEs need to be filed as appropriate.

Re-initiation of the study drug can only be considered if the macular edema has resolved completely, the individual risk-benefit is favorable (as determined by the Investigator, in agreement with the Ophthalmologist) and after discussion with the Novartis Medical Advisor. The patients must have follow up ophthalmic examinations at one month after study drug is re-initiated, three months later and then every 3 months up to one year, and every 6 months thereafter.

For participants discontinuing study drug for any of the above ophthalmic reasons, copies and source documents of the related ophthalmic examination should be kept at the site as source documents. These documents may need to be submitted for review by an independent panel if needed.

Guidance on monitoring patients with uveitis

Participants with a history of uveitis or findings compatible with active uveitis at baseline can enter the study given that there is no evidence of macular edema in the baseline ophthalmic examination.

In order to specifically assess the risk of macular edema in the MS population with coexisting uveitis, each participant with findings in any ophthalmic examination compatible with active uveitis (e.g., significant anterior chamber cell or flare, vitreous cell or flare, pars planitis, vasculitis, chorioretinitis) under the discretion of the investigator should undergo an ophthalmic examination. It is the discretion of the investigator to determine the frequency of these ophthalmic examinations. Adjustments to the schedule can be made to align these evaluations with other planned study visits.

The diagnosis of macular edema may lead to study drug interruption. But the decision on whether or not fingolimod therapy should be interrupted needs to take into account the potential benefits and risks for the individual participant.

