8.4.4.2 Ophthalmic examination

A complete ophthalmic examination will be performed by an ophthalmologist as described in [Table 8-1](#).

At Screening and Month 3, Best Corrected Visual Acuity (BCVA) and Optical Coherence Tomography (OCT) for the measurement of central foveal thickness will be collected.

At all other scheduled visits, BCVA and new ophthalmic symptoms will be collected. In the case of confirmed visual acuity decline, an optical coherence tomography will be conducted by the investigator's discretion.

Details on the ophthalmic examinations are provided in the Guidance for Ophthalmic Monitoring [Section 16.6](#).

The ophthalmologist will describe examination findings on an examination worksheet provided by the investigative site. The worksheet will be transferred to the site where the data will be transcribed to the Ophthalmic Examination eCRF.

Participants with newly diagnosed uveitis after initiation of study drug will require more frequent ophthalmic evaluations. Refer to [Section 16.6](#) for the Guidance for Ophthalmic Monitoring for details on monitoring of participants with uveitis during the study.

During the study, participants with a diagnosis of macular edema must interrupt the study drug. These patients must be followed-up 1 month and 3 month after diagnosis of macular edema and more frequently if needed based on the ophthalmologist's judgement. Further ophthalmologic evaluations until such time as resolution is confirmed or no further improvement is expected by the ophthalmologist (based on a follow up period of not less than 3 months). If the participant does not show definite signs of improvement on examination by specialist testing (e.g. OCT, FA) 6-8 weeks after interruption of study drug, then therapy for macular edema in conjunction with an ophthalmologist experienced in the management of this condition should be initiated.

Re-initiation of the study drug can only be considered if the macular edema has resolved completely, the individual risk-benefit is favorable (as determined by the Investigator, in agreement with the Ophthalmologist) and after discussion with the Novartis Medical Advisor.

The patients must have follow up ophthalmic examinations at one month after study drug is re-initiated, three months later and then every 3 months up to one year, and every 6 months thereafter.

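### For participants with uveitis, the protocol makes study drug interruption on a diagnosis of macular edema both mandatory and discretionary, and states no exception

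*Protocol*

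**What the plan says.** Three places in the protocol deal with study drug after a diagnosis of macular edema.

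- **Section 8.4.4.2, Ophthalmic examination:** "participants with a diagnosis of macular edema must interrupt the study drug".
- **Section 16.6 (Appendix 6), general guidance:** "participants with a diagnosis of macular edema during the study must interrupt the study drug". On restarting: "Re-initiation of the study drug can only be considered if the macular edema has resolved completely". A favourable individual risk-benefit assessment and a discussion with the sponsor's medical advisor are further conditions. Section 8.4.4.2 has the same restart conditions.
- **Section 16.6 (Appendix 6), guidance on uveitis, closing paragraph:** "The diagnosis of macular edema may lead to study drug interruption". The next sentence says that the decision "whether or not fingolimod therapy should be interrupted needs to take into account the potential benefits and risks" for the individual participant.

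Uveitis is not a bar to entry. Appendix 6 says: "Participants with a history of uveitis or findings compatible with active uveitis at baseline can enter the study", provided that the baseline examination shows no macular edema. The same appendix says: "Patients with history of uveitis and patients with diabetes mellitus are at an increased risk of macular edema", and Section 1.1 makes the same point about uveitis. For participants with newly diagnosed uveitis, Section 8.4.4.2 asks for more frequent eye examinations and refers sites to Section 16.6 "for the Guidance for Ophthalmic Monitoring for details on monitoring of participants with uveitis during the study".

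**The concern.** In the first two places, interruption follows automatically from the diagnosis, and benefit-risk is considered only once the edema has fully resolved. In the third, benefit-risk decides whether to interrupt at all. The same act cannot be both required and optional for the same participant, and nothing in the current text says which instruction prevails.

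Macular edema is an adverse event of special interest (Section 8.4.5), and Section 1.1 reports that it generally improved or resolved after the drug was stopped. A participant with uveitis could be kept on drug under the looser wording. The management pathway would then lose its starting point, because Section 8.4.4.2 and Appendix 6 time the decision to treat the edema at 6 to 8 weeks after interruption. It would also be unclear whether continued dosing is a protocol deviation, although Section 14 expects investigators to avoid deviations.

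**Working it through.** The conflict itself is textual, so the check is a side-by-side reading.

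| Question | Section 8.4.4.2 | Appendix 6, general | Appendix 6, uveitis |
|---|---|---|---|
| Is interruption required on diagnosis? | Yes | Yes | Possible, not required |
| Where does benefit-risk enter? | Restart only | Restart only | The interruption decision |
| Is uveitis excepted? | No | No | Not stated |
| Does it claim precedence? | No | No | No |

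1. A participant with past or active uveitis may enrol, so all three texts can apply to one person.
2. If the site interrupts, it complies with all three.
3. If the site weighs benefit and risk under the uveitis guidance and continues dosing, it complies with that guidance and breaks the other two.
4. The reference from Section 8.4.4.2 to Section 16.6 concerns monitoring. It does not announce a different rule for drug action.

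The plan has no figure of its own to reproduce here. The likely number of affected participants can be bounded.

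**Macular edema in any participant.** The inputs are a rate of 0.5% at 0.5 mg/day (Section 1.1) and about 100 participants (Section 3).

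- Expected cases: 100 × 0.005 = 0.5
- Chance of at least one: 1 − 0.995^100 = 0.394

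**Macular edema together with uveitis.** The documents give neither the frequency of uveitis nor the size of the added risk. The assumed inputs are 1 to 5 participants with uveitis, each with a macular edema risk of 0.5% to 5%.

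- Low end: 1 × 0.005 = 0.005 expected cases; chance of at least one = 0.005
- High end: 5 × 0.05 = 0.25 expected cases; chance of at least one = 1 − 0.95^5 = 0.226
- Intermediate illustration: the only multiplier in the documents is two-fold, from renal transplant settings (Section 1.1 and Appendix 6). Doubling 0.5% to 1% in 5 participants gives 5 × 0.01 = 0.05 expected cases; chance of at least one = 1 − 0.99^5 = 0.049

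**The case against.** The strongest defence is that the uveitis text is a specific rule that displaces the general one, or that it is only permissive: it never tells a site to continue dosing, and a site that interrupts satisfies every instruction. The mandatory rule appears twice, once in the main body, and in Appendix 6 it comes before the uveitis guidance, so a site reading in order meets it first. The permissive sentences do not themselves mention uveitis. Their restriction to that group is inferred from their position under the heading, and they could be a general closing remark. Section 9.1.1 already requires treatment to stop where continuing might pose a safety risk, and macular edema at screening is an exclusion (Section 5.2, criterion 7). The numbers for uveitis are assumptions, zero such participants is plausible, and even at the upper end no case is the likeliest outcome.

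The rarity and the weakness of the numbers stand. The rest does not remove the conflict. No text declares a special rule, and such a rule would give the looser instruction to the group that the protocol calls higher risk. If an exception was intended, Section 8.4.4.2 and the general guidance are wrong for omitting it, so an edit is needed either way. If the sentences are a general remark, the conflict reaches every participant, and replacing them still resolves it. Section 9.1.1 depends on a judgement of risk and does not rank the instructions; the screening exclusion does not cover edema that develops on treatment.

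**Conclusion.** The concern holds: the text is wrong as written. Two statements require interruption, one leaves it to judgement, and no exception or order of precedence connects them. The reading is taken to affect participants with uveitis, because the permissive sentences sit under that heading.

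The practical size is small. Under the assumed 1 to 5 participants with uveitis and a risk of 0.5% to 5% each, the chance that anyone is affected runs from 0.5% to about 23%. The upper figure rests wholly on assumed inputs. The annualized relapse rate estimate is not affected. The point should be corrected because a participant's sight may be at stake and the correction is cheap.

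**What to change.** Replace the last two sentences of the uveitis guidance in Appendix 6 with: *Participants with uveitis who are diagnosed with macular edema must interrupt the study drug; individual benefit-risk is considered only for re-initiation, under the conditions above.* Section 8.4.4.2 and the general part of Appendix 6 stay unchanged. If the sponsor did intend a uveitis exception, the alternative is to state it expressly in both of those places. Alignment is preferable because it follows the rule already given twice.

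The cost is a short written amendment approved by the sponsor, the IRB/IEC and, where required, health authorities, plus a letter to sites. Section 14.1 allows a change required for participant safety to take effect at once, with notification afterwards.

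The documents do not say whether dosing has ended. The latest SAP amendment is dated April 2025, before final database lock, so it may have. In that case an amendment has no use, and the clinical study report should state which rule governed any macular edema case. The listing of macular edema cases planned in SAP Section 2.8.4.3 is a natural place for this.

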16.7 Appendix 7 Guidance on safety monitoring

Guidance on monitoring of patients with elevated blood pressure

Participants who have at least two out of the three sitting readings of blood pressure (systolic BP ≥ 140 and/or diastolic BP ≥ 90 mmHg) should be recommended referred to his primary care physician, an independent internist or to the specialty hypertension clinic for evaluation, diagnosis and treatment of hypertension. Participants with BP values of $> 160/100$ mmHg on any visit during the study should be immediately referred as above for evaluation, diagnosis and treatment of hypertension. Newly diagnosed hypertension as well as an aggravation of a pre-existing condition must be reported as an AE and discontinuation of the study drug may be considered by the investigator.

Guidance on monitoring of participants with elevated liver function tests

Table 16-3 Liver event and laboratory trigger definitions

	Definition/ threshold
Liver laboratory triggers If ALT, AST and total bilirubin normal at baseline:	
 ALT or AST $> 5 \times$ ULN ALP $> 2 \times$ ULN (in the absence of known bone pathology) Total bilirubin $> 3 \times$ ULN (in the absence of known Gilbert syndrome) ALT or AST $> 3 \times$ ULN and INR > 1.5 Potential Hy's Law cases (defined as ALT or AST $> 3 \times$ ULN and Total bilirubin $> 2 \times$ ULN [mainly conjugated fraction] without notable increase in ALP to $> 2 \times$ ULN) Any clinical event of jaundice (or equivalent term) ALT or AST $> 3 \times$ ULN accompanied by (general) malaise, fatigue, abdominal pain, nausea, or vomiting, or rash with eosinophilia Any adverse event potentially indicative of a liver toxicity*
If ALT or AST abnormal at baseline:	
 ALT or AST $> 2 \times$ baseline or > 300 U/L (whichever occurs first)

*These events cover the following: hepatic failure, fibrosis and cirrhosis, and other liver damage-related conditions; non-infectious hepatitis; benign, malignant and unspecified liver neoplasms ULN: upper limit of normal

During clinical trials, elevations 3 times the upper limit of normal (ULN) or greater in liver transaminases occurred in 8% of patients treated with fingolimod 0.5 mg compared to 2% of placebo patients. Elevations of 5 times the upper limit of normal occurred in 2% of patients on fingolimod and 1% of patients on placebo. Serum transaminase levels returned to normal within approximately 2 months after discontinuation of fingolimod.

If repeat ALT/AST values reach 5 times the ULN, the study drug will be interrupted until the results return within the normal range. More frequent monitoring should be instituted, including serum bilirubin, alkaline phosphatase (ALP) and other evaluations per discretion of the investigator. The study drug may be re-started once results return within normal range and per discretion of the investigator.

Patients who develop symptoms suggestive of hepatic dysfunction, such as unexplained vomiting, abdominal pain, fatigue, anorexia, jaundice or dark urine, should have liver enzymes checked, and fingolimod should be discontinued if significant liver injury is confirmed. Re-initiation of study drug will be dependent on whether or not another cause of liver injury is determined, and on the benefits to the patient of resuming therapy versus the risks of recurrence of liver dysfunction and per the discretion of the investigator.

More frequent liver monitoring may be instituted based on the clinical judgement in the below condition:

- For participants with normal ALT and AST and TBIL value at baseline: detection of elevated ALT/AST values of $>3.0 \times$ ULN and total bilirubin $> 2.0 \times$ ULN
- For participants with elevated AST or ALT or TBIL value at baseline: detection of elevated [AST or ALT $> 2 \times$ baseline] OR [AST or ALT $> 300\text{U/L}$] (whichever occurs first) combined with [TBIL $> 2 \times$ baseline AND $> 2.0 \times$ ULN]

Patients should be monitored for signs and symptoms of any hepatic injury. Measure liver transaminase and bilirubin levels promptly in patients who report symptoms that may indicate liver injury, including new or worsening fatigue, anorexia, right upper abdominal discomfort, dark urine, or jaundice. In this clinical context, if the patient is found to have ALT/AST values of $>3.0 \times$ ULN with total bilirubin $> 2.0 \times$ ULN, treatment with fingolimod may be interrupted based on the clinical judgement. Treatment should not be resumed if a plausible alternative etiology for the signs and symptoms cannot be established, because these patients are at risk for severe drug-induced liver injury.

Because fingolimod exposure is doubled in patients with severe hepatic impairment, these patients should be closely monitored, as the risk of adverse reactions is greater.

Re-initiation of the study drug shall be considered once the liver enzymes are within the normal reference range and/or patients have clinically recovered from liver injury signs based on your clinical judgement, and kindly reach out to Medical Advisor at Novartis for any further clarification. In case it is agreed to re-start the study drug, weekly liver function test may be performed for patient's safety. Advise patients that they should contact their physician if they have any unexplained nausea, vomiting, abdominal pain, fatigue, anorexia, or jaundice and/or dark urine. The deterioration of new elevations above 2 times the ULN with worsening of liver injury clinical signs/symptoms based on investigator's clinical judgement may lead to permanent discontinuation of study drug in the best interest of patient's safety.

An interruption or discontinuation of the study drug should be clearly documented and reflected on Dosage Administration Record eCRF. AE/SAEs need to be filed as appropriate.

Guidance on monitoring of participants with notable lymphopenia

Fingolimod results in sequestration of a proportion of the circulating lymphocytes in lymph nodes with resultant reduction in circulating lymphocyte counts. Average circulating lymphocytes counts are expected to be around $0.5\text{-}0.6 \times 10^9/\text{L}$ or $500\text{-}600 \text{ cells/mm}^3$. Please see Investigator Brochure for more details. As such, the absolute total WBC, neutrophil and lymphocyte counts will be measured at each visit by the local laboratory. In case of lymphocyte alert, lymphocyte count should be repeated in two weeks by the local laboratory. If the repeat test confirms the lymphocyte count is below $0.2 \times 10^9/\text{L}$ or 200 cells/mm^3 , the study drug must be interrupted and the lymphocytes count needs to be monitored every two weeks until levels reach around $0.5\text{-}0.6 \times 10^9/\text{L}$ or $500\text{-}600 \text{ cells/mm}^3$ values. Recovery of lymphocyte counts is expected to take several weeks given the long half life of fingolimod. The participant should be evaluated and monitored for infections on a regular basis during this period.

Re-initiation of the study drug can only be considered once the lymphocyte counts is around $0.5\text{-}0.6 \times 10^9/\text{L}$ or $500\text{-}600 \text{ cells/mm}^3$ as confirmed by the local lab, for further detailed information please refer to the latest Investigator Brochure or label of fingolimod.

Guidance on monitoring of participants with symptoms of neurological deterioration, inconsistent with MS course

Should a participant develop any manifestations that, in opinion of the investigator, are atypical for multiple sclerosis including unexpected neurological or psychiatric symptom/signs (e.g. rapid cognitive decline, behavioral changes, cortical visual disturbances or any other neurological cortical symptoms/sign), or any symptom/sign suggestive of an increase of intracranial pressure or accelerated neurological deterioration, the investigator may schedule a complete physical and neurological examination and an MRI as soon as possible and before beginning any steroid treatment. Conventional MRI as defined in the protocol as well as Fluid-attenuated Inversion Recovery (FLAIR) and Diffusion-weighted imaging (DWI) sequences are recommended for differential diagnosis of posterior reversible encephalopathy syndrome. The MRI must be evaluated by the local neuro-radiologist and investigator. The investigator will contact the Medical Representative at Novartis to discuss findings and diagnostic possibilities as soon as possible. AE/SAEs need to be filed as appropriate.

In case of new findings in the MRI images in comparison with the previous available MRI which are not compatible with MS lesions, the study drug will be interrupted and other diagnostic evaluations need to be performed at the discretion of the investigator. In case of presence of new hyper-intense T2-weighted lesions in the MRI which may be infectious in origin it is recommended to collect a cerebrospinal fluid sample if indicated. Analysis of the CSF sample including cellular, biochemical and, microbiological analysis ((e.g. herpes virus, John Cunningham virus (JC virus)), to confirm/exclude an infection ((e.g. progressive multifocal leukoencephalopathy (PML)) should be performed.

Only when the differential diagnosis evaluations have excluded other possible diagnosis than MS and after discussion with the Medical Representative at Novartis, the study drug may be restarted.

Guidance on monitoring of participants with infections

Initiation of treatment with Fingolimod should be delayed in patients with severe active infection until resolution. If a patient develops a serious infection, suspension of Fingolimod should be considered and consideration of benefit-risk should be undertaken prior to re-initiation of therapy.

All infections that develop during the study will be reported as AEs. Investigators are requested to specifically ask about infections at each visit. Treatment and additional evaluations will be performed at discretion of the investigator.

The investigator should remind the participant of the risk of infections and to instruct them to promptly report any symptoms of infections to the investigator.

The investigator should consider early treatment with specific antimicrobial therapy on the basis of clinical diagnosis or suspicion thereof (e.g. antiviral treatment for herpes simplex or zoster) in consultation with infectious disease experts, as appropriate. The investigator should inform the Novartis medical expert of any such cases.

Investigators should consider the added immunosuppressive effects of corticosteroid therapy for treatment of MS attack/relapse and increase vigilance regarding infections during such therapy and in the weeks following administration.

It is also important to ask the patient to report if they are exposed to anyone who has recently received a live or live attenuated vaccine and manifested a skin rash after the vaccination so that it can be decided, in consultation with an infectious disease expert, if antiviral therapy is warranted.

It should be noted that live or live attenuated vaccines are prohibited while patients are taking study drug and for 2 months after study drug discontinuation. They may be administered, thereafter, once there is confirmation that lymphocyte counts are in the normal range.

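### Section 16.7 leaves interruption optional for liver symptoms with ALT/AST >3 × ULN and bilirubin >2 × ULN, which conflicts with its own risk statement and the stop rules around it

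*Protocol*

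**What the plan says.** All of the specific stopping text is in Protocol Section 16.7, in the guidance on elevated liver function tests.

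- **Enzymes alone.** "If repeat ALT/AST values reach 5 times the ULN, the study drug will be interrupted until the results return within the normal range". Restart is permissive: "The study drug may be re-started once results return within normal range and per discretion of the investigator".
- **Symptoms suggesting hepatic dysfunction.** Enzymes are to be checked, and "fingolimod should be discontinued if significant liver injury is confirmed". No threshold is attached to that term.
- **Symptoms plus ALT/AST >3 × ULN plus total bilirubin >2 × ULN.** Here "treatment with fingolimod may be interrupted based on the clinical judgement". The restart condition is strict: "Treatment should not be resumed if a plausible alternative etiology for the signs and symptoms cannot be established". The protocol gives its reason in the same sentence: "because these patients are at risk for severe drug-induced liver injury".

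Three other places bear on the question. Section 9.1.1 requires discontinuation where continuing might pose a safety risk, and obliges the investigator to stop if continuing is believed harmful. Section 10.2.1 asks that interruption be considered once an elevation is confirmed. Section 6.5.2.1 requires close follow-up of combined enzyme and bilirubin rises, and SAE reporting of confirmed cases with no other cause. It has no dosing rule.

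**The concern.** The protocol sets its strictest restart condition for the symptomatic pattern with raised bilirubin, and gives severe DILI as the reason. Yet the sentence on stopping for that pattern is permissive, while a repeat enzyme rise to 5 × ULN carries a firm stop. A bar on resuming does nothing for a participant whose dosing was never interrupted.

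The stake is participant safety, not the estimate. Transaminase elevation is a known risk of the drug: Section 1.1 reports rises of at least 3 × ULN in 8.0% on 0.5 mg against 1.9% on placebo. Section 8.4.4.4 says elimination may take up to two months, so a late stop is slow to take effect. With around 10 to 15 centers each applying judgement (Section 5), similar cases could be handled differently.

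**Working it through.** The plan gives no figure to reproduce. The check sets the rules side by side.

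| Place | Trigger | Repeat value needed? | Action on drug |
|---|---|---|---|
| 16.7, enzymes alone | ALT/AST at 5 × ULN | Yes | Will be interrupted |
| 16.7, combined pattern | Symptoms, ALT/AST >3 × ULN, bilirubin >2 × ULN | No, acts on values as found | May be interrupted |
| 16.7, symptomatic | Significant liver injury (undefined) | Must be confirmed | Should be discontinued |
| 9.1.1 | Any situation that might be a safety risk | Not stated | Discontinuation required |
| 10.2.1 | Liver event with confirmed elevation | Yes | Interruption to be considered |
| 6.5.2.1 | ALT/AST >3 × ULN with bilirubin >2 × ULN | For SAE reporting only | None stated |

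**Step 1: where the rules part.** If repeat ALT/AST reaches 5 × ULN, the firm rule applies to everyone, symptomatic or not. What is left is the symptomatic pattern whose enzymes are above 3 × ULN but stay below 5 × ULN on repeat, and any such case before the repeat result is known.

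**Step 2: like with like.** On a first value, neither specific rule compels a stop. On a confirmed value, the enzyme rule compels interruption. For the symptomatic pattern, a stop follows only if the investigator decides that the finding is significant liver injury or a safety risk. Nothing in 16.7 says the >3 ×/>2 × pattern meets either description.

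**Step 3: practice elsewhere in the protocol.** Firm wording is used for diagnosed macular edema (8.4.4.2 and the main text of 16.6), for confirmed lymphocytes below 0.2 × 10⁹/L, and for new MRI findings not compatible with MS (both 16.7). The uveitis paragraph of 16.6 is softer.

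**Step 4: size.** Only an enzyme figure can be computed. From Section 1.1, 8.0% (≥3 × ULN) − 1.8% (≥5 × ULN) = 6.2%, or about 6 of 100 participants. The rounded rates in 16.7 give 8% − 2% = 6%. If no value at or above 5 × ULN were confirmed on repeat, the figure would be 8.0%, or 8 of 100. These are not estimates of the gap. Section 1.1 calls the rises asymptomatic, whereas the gap requires symptoms and bilirubin >2 × ULN as well. The documents give no rate for that combination.

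**The case against.** A reader might infer that the protocol's stopping rules run opposite to its own ranking of risk, or that it has no stop for this pattern. The documents do not support either reading, for three reasons.

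- Section 9.1.1 is mandatory, and 16.7 itself names the pattern as a risk. Read together, they leave little room to go on dosing an unexplained case.
- The 5 × ULN rule acts on a repeat value, while the permissive sentence acts on values as found. At a first value that sentence, if anything, invites earlier action.
- Once injury is confirmed in a symptomatic participant, 16.7 speaks of discontinuation, which is stronger than interruption. Section 6.5.2.1 makes confirmed unexplained cases SAEs, so an investigator would hardly call them insignificant.

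There are also reasons for leaving room for judgement. Section 6.5.2.1 treats DILI as a diagnosis of exclusion. Amendment 01 says the liver guidance was revised to follow the China label, which is not available here, so the permissive word may be deliberate. A firm stop before confirmation would also be stricter than the 5 × ULN rule, so it goes beyond restoring consistency.

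What stands is that a stop is likely and that the enzyme percentages do not measure the problem. What does not follow is that the text is adequate. The general clauses set no threshold for this pattern, and the only sentence that addresses stopping for it is discretionary and sits beside a statement of serious risk. A label origin could explain the conflict but would not remove it.

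**Conclusion.** Section 16.7 is internally inconsistent on stopping drug for the symptomatic DILI pattern. The specific rule permits what the surrounding text expects. This is a cheap improvement to a safety rule, not an error that threatens the study.

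The frequency is unknown and may be zero, so the case rests on how serious a single event would be. It assumes that sites follow the specific sentence in preference to the general clauses, and that the label does not dictate the permissive wording. The latest SAP amendment, dated 2 April 2025, precedes final database lock. Dosing may therefore be over; the documents do not say. That limits what a change could still do, not whether the text conflicts.

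**What to change.** Make two wording changes in Section 16.7, after checking both against the current China label.

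1. In the combined-pattern sentence, replace the permissive clause with: *must be interrupted pending prompt repeat testing and the causality work-up in 6.5.2.1*. Where baseline values are raised, use the criteria already given in 6.5.2.1 and 16.7 under "For participants with elevated AST or ALT or TBIL value at baseline". Except known Gilbert syndrome, as Table 16-3 does for its isolated-bilirubin trigger ("in the absence of known Gilbert syndrome"). Direct bilirubin is already on the chemistry panel in Table 8-3.
2. State that significant liver injury includes this symptomatic pattern when confirmed on repeat.

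No change is proposed for asymptomatic Table 16-3 cases, monitoring frequency or Section 10.2.1.

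**Cost.** No new scheduled assessments are needed. There would be a rare extra interruption, sometimes before confirmation and sometimes permanent because of the resumption bar. First-dose monitoring is repeated after a gap of 1 day or more in the first 2 weeks, more than 7 days in weeks 3 and 4, or more than 14 days after the first month (8.4.4.1). After a permanent stop, MRI scans more than 30 days beyond the last dose are dropped (SAP 2.7, 2.7.3). Relapse follow-up could also shorten if the end of treatment period date is recorded as the discontinuation date (SAP 2.1.1, 2.5.1), even though SAP 2.5.3 counts data on or off treatment up to that date. The analysis method does not change.
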